## 12.9 Halting Rules for the Protocol

Halting the study requires immediate discontinuation of study agent administered for all participants and suspension of enrollment until a decision is made whether or not to continue enrollment and study agent administration.

The halting rules are:

- 1 or more participants experience the same or similar SAEs that are possibly, probably, or definitely related to the study agent;

OR

- 2 or more of the same or similar AE in different participants that are grade 3 or above and are possibly, probably, or definitely related to the study agent;

OR

- Any safety issue that the PI and/or the CSO determines should halt the study.

The PI and/or CSO will determine if the study should be halted. In addition, the FDA may halt the study at any time following review of any safety concerns.

### 12.9.1 Reporting a Study Halt

If a halting rule is met, a description of the AE(s) or safety issue must be reported by the PI or designee within 1 business day to the Co-Investigator, IND Sponsor, CSO, the IRB, and the DSMB by fax or email.

### 12.9.2 Resumption of a Halted Study

The IND sponsor, in collaboration with the PI and the DSMB will determine if it is safe to resume the study. The PI will notify the IRB of the decision on resumption of the study.

Participants who do not resume study agent will continue to be followed for safety.

## 12.10 Study Discontinuation

Office of Clinical Research Policy and Regulatory Operations (OCRPRO), the study sponsor, the IRB, and the FDA have the right to terminate this study at any time. Reasons for terminating the study may include, but are not limited to, the following:

1. The incidence or severity of AEs in this study indicates a potential health hazard to participants
2. Participant enrollment is unsatisfactory
3. Data recording is inaccurate or incomplete
4. Investigators do not adhere to the protocol, or applicable regulatory guidelines in conducting the study

The IRB, the NIAID, the FDA, or other government agencies, as part of their duties to ensure that research participants are protected may discontinue the study at any time. Subsequent review of serious, unexpected and related AEs by the IRB, the DSMB, the sponsor, the FDA, and other regulatory

authorities may also result in suspension of further trial interventions/administration of study agent at a site. The FDA, other regulatory authorities, and the study sponsor retain the authority to suspend additional enrollment and study agent administration for the entire study as applicable.

### **12.11 Premature Withdrawal of a Participant**

Participants may withdraw before vaccine administration and no further testing or follow-up will be performed. The PI or designee will discuss with the participant why she/he wants to prematurely withdraw from the study to determine the best course of action for the participant. If the participant would like to withdraw after vaccination, clinical laboratory tests and procedures for safety purposes will continue as obtainable and at a frequency determined by the PI. If the participant does not return for scheduled follow-up visits, the study staff will make every reasonable effort to contact the participant by phone, mail, or email, or a combination of the latter and reiterate that follow-up visits are strongly encouraged for safety reasons.

An individual participant will be withdrawn for any of the following:

- An individual participant's decision. (The investigator should attempt to determine the reason for the participant's decision.)
- Non-compliance with study procedures to the extent that it is potentially harmful to the participant or to the integrity of the study data.
- A change in the participant's baseline condition after enrollment so that the participant no longer meets one or more of the inclusion/exclusion criteria.
- The investigator determines that continued participation in the study would not be in the best interest of the participant.

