#### **4.6 Reasons for Withdrawal**

Participants are free to withdraw from the study at any time. Participants will be encouraged to remain in the study to be followed for safety purposes.

A study participant will be discontinued from participation in the study for any one of the following reasons:

- Request by participant to terminate participation;
- Loss to follow-up;
- Request of primary care provider;
- At the request of the IRB/Ethics committee, NIH, NIAID, or the U.S. Food and Drug Administration (FDA);
- The participant’s well-being, based on the opinion of the investigator.

Because a true intent-to-treat analysis requires the inclusion of all participants enrolled to the extent possible, this requires an intent-to-treat design in which all participants are followed according to the pre-specified schedule with primary, and perhaps secondary, outcome assessments, regardless of compliance, adverse effects, or other post-enrollment observations— participant refusal excepted.

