#### **4.7 Handling of Withdrawals**

If voluntary withdrawal occurs, the participant will be asked for permission to continue scheduled evaluations, complete an end-of-study evaluation, and be given appropriate care under medical

supervision until the symptoms of any adverse event resolve or until the participant's condition becomes stable.

It is vital to collect safety data on any participant discontinued because of an AE or SAE, and every effort will be made to undertake protocol-specified safety follow-up procedures. Participants will follow early termination procedures if withdrawn.

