## 6.4 Day 22 (+/- 3 days) (outpatient visit)

The second study vaccine administration will take place if the participant continues to meet all inclusion and none of the exclusion criteria following these procedures:

- Review of medical/medication history
- Targeted physical exam/assessment as needed

- Vital signs (temperature, heart rate, blood pressure)
- Vital signs at least 30-45 minutes post vaccination
- Blood collection for routine safety labs (Hemoglobin, white blood cell count, platelets, serum creatinine, serum alanine aminotransferase, random glucose)
- Urine pregnancy test (females of childbearing potential only)
- Vaccine or placebo administration
- Vaccine injection site reaction and AE assessment pre-vaccination and at least 30-45 minutes post vaccination
- AE memory aid, thermometer, and ruler will be distributed before discharge home if the previous set is lost

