#### 12.4.4 Pregnancy

All pregnancies will be reported on the Pregnancy Notification/Outcome Form to the CSO within 1 business day from site awareness.

Pregnancy outcome data (e.g., delivery outcome, spontaneous or elective termination of the pregnancy) will be reported to the CSO within 3 business days of the site's awareness.

Although pregnancy itself is not an AE, events that meet SAE criteria during pregnancy, delivery, or in the neonate (e.g., congenital anomaly/birth defect) are reportable on the SERF.

In the event of pregnancy, the following steps will be taken:

- Discontinue the study agent and procedures but continue to follow-up for safety.
- Report to the Data and Safety Monitoring Board (DSMB) and the IRB.
- Advise the research participant to notify the obstetrician of study participation and study agent exposure.

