### **12.12 Replacement of a Participant**

If a participant withdraws or appears ineligible to continue the study before vaccine/placebo administration, he/she will be removed and no data will be used in analysis or publication of the study. The participant may be replaced in the accrual with a new volunteer who qualifies and consents to the study, and who can complete both vaccinations 14-28 days before the planned date of mosquito challenge. Safety data from all participants that have withdrawn will be used and included in the safety analysis.

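### Withdrawal for lost eligibility (12.11) conflicts with following every participant for primary outcomes (4.6), and a failed Day 22 re-check can cost the Day 43 immunogenicity sample

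*Combined protocol and SAP*

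**What the plan says.** Five parts of the protocol bear on a participant who has had dose 1 and then stops meeting a criterion.

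- **6.4 (Day 22).** "The second study vaccine administration will take place if the participant continues to meet all inclusion and none of the exclusion criteria". Only the injection is made conditional on the re-check.
- **12.11.** Withdrawal is mandatory for several reasons. One is a change in the participant's "baseline condition after enrollment so that the participant no longer meets one or more of the inclusion/exclusion criteria".
- **4.7.** "If voluntary withdrawal occurs, the participant will be asked for permission to continue scheduled evaluations". For withdrawal in general: "Participants will follow early termination procedures if withdrawn". Those procedures are not set out.
- **4.6.** A true intent-to-treat analysis "requires the inclusion of all participants enrolled to the extent possible", so all participants are "followed according to the pre-specified schedule with primary, and perhaps secondary, outcome assessments, regardless of compliance, adverse effects, or other post-enrollment observations", with refusal the only stated exception. The list of discontinuation reasons in 4.6 includes the participant's well-being in the investigator's opinion, but not loss of eligibility as such.
- **12.12.** "Safety data from all participants that have withdrawn will be used and included in the safety analysis". Replacement is provided only for losses before any vaccine or placebo is given.

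The antibody and cytokine primary endpoints in 3.2 run from Day 1 to Day 43, so they need a sample taken after the Day 22 check.

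**The concern.** Withholding dose 2 from someone who no longer qualifies is not in dispute. The problem is what happens to that person's outcome data. Under 12.11 the participant leaves the study; under 4.6 the participant stays on schedule for primary outcomes. Many failed criteria would not make a blood draw unsafe. An acute skin condition on Day 22 (exclusion 20) is a simple example.

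At stake is the randomized immunogenicity comparison. If participants leave it because of something that happened after dose 1, the missing data may be selective, which is what 4.6 sets out to avoid. With 10 per arm, each missing value counts. The safety endpoint is largely protected, because 12.12 keeps safety data from withdrawn participants.

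**Working it through.** **Step 1: trace one participant through the text.** The participant receives dose 1 on Day 1 and fails the re-check on Day 22.

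1. Under 6.4, no second injection is given.
2. Under 12.11, if the failure is a change in baseline condition, the participant is withdrawn.
3. Under 4.7, undefined early termination procedures follow. The request to continue scheduled evaluations is tied to voluntary withdrawal, which this is not.
4. The only follow-up that 12.11 describes after vaccination is for safety, at a frequency the investigator sets.
5. Section 6.9 promises at least 12 months of follow-up, but the contacts it adds are telephone calls on Days 181 and 366, without research blood.
6. Under 12.12, the safety data are kept and the participant is not replaced.

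Nothing in this chain provides the Day 43 research draw, which Appendix B puts at 4 mL serum + 50 mL whole blood = 54 mL. Without it there is no Day 1 to Day 43 fold increase. Section 4.6 would keep the draw, but no section gives it precedence. Section 14 defines no immunogenicity analysis population that would settle the matter.

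**Step 2: Groups 1 and 3.** By 3.1 and 5.4, both receive saline on Day 22. A Group 3 participant withdrawn that day has already had the whole active regimen, and a placebo participant was never due any. Losing their Day 43 samples has no dosing rationale. Because staff are blinded, the rule would be applied to these groups like any other.

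**Step 3: power cost.** Inputs from 14.2 are 10 per arm, a difference of 0.95 SD and a one-sided t-test at 0.1. With df = n1 + n2 − 2 and noncentrality = 0.95 / √(1/n1 + 1/n2), power is the probability that a noncentral t exceeds the 90th percentile of the central t.

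- 10 v 10: noncentrality 0.95/√0.2 = 2.12, df 18, power **78.6%** (normal approximation 80.0%). Section 14.2 states at least 85%, which this does not reproduce. That is a separate matter; 78.6% is used here as the baseline.
- 9 v 10: noncentrality 0.95/√0.2111 = 2.07, df 17, power **76.9%**.
- 8 v 10: 74.8%. 7 v 10: 72.3%.

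The first loss in one arm costs 78.6 − 76.9 = 1.7 points. The numbers of losses are assumptions: the documents give neither a Day 22 failure rate nor a dropout allowance.

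**Step 4: possible bias.** If one of 10 values lies k SD from its arm mean and is removed, the mean of the remaining nine moves by k/9 SD. For k = 1 that is 0.11 SD, and for k = 2 it is 0.22 SD. This is illustrative only. If removal is unrelated to response, the expected shift is zero, and the documents do not show which case applies.

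**The case against.** **The sections can be read together.** Section 6.4 makes only the injection conditional. Section 4.6 states a general follow-up rule. The safety-only sentence in 12.11 is written for participants who want to leave. The trigger is a change in baseline condition, which need not cover every failed item. On this reading one stops study agent and keeps the schedule. This part of the objection stands: a reader might infer that the protocol orders the Day 43 draw to be dropped, and it does not. But the reading has to be constructed. Withdrawal is mandatory in 12.11, and no text reserves the draw for participants so withdrawn. Where the protocol does separate stopping agent from follow-up, as for pregnancy in 12.4.4, it says so: "Discontinue the study agent and procedures but continue to follow-up for safety".

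**A tempting stronger claim fails.** A reader might treat a severe reaction to dose 1 as meeting exclusion 13 (prior severe immunization reaction) and apply the FLU-v phase 2b counts in 8.2: 5/57 adjuvanted, 1/58 non-adjuvanted, 0/32 non-adjuvanted placebo. That gives 1 − (52/57)^10 = 60% for at least one removal in a Montanide arm. The documents do not support this as an estimate:

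- Reactions to study agent have their own rules. Section 12.8 pauses dosing for a related SAE, for two related events of Grade 3 or above, or on investigator judgment, and provides a decision on resumption. Automatic withdrawal after one severe local reaction would leave those provisions little purpose.
- At 5/57, two or more such events among the 20 Montanide participants have probability 1 − (52/57)^20 − 20(5/57)(52/57)^19 = 53%. If the reactions were similar, that would also meet the second halting rule in 12.9.
- Section 8.2 says the severe reactions resolved with over-the-counter treatment. The 1/58 arm received two doses. The AGS-v summary describes mild safety issues. The contrast 5/57 v 0/32 has Fisher p = 0.16.

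**The choice of primary analysis is the sponsor's.** Primary objective 2 concerns participants receiving two doses, apart from the single-dose Montanide arm. Whether one-dose participants belong in the primary analysis is an estimand question that this conflict does not settle. That stands.

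**Conclusion.** The conflict between 12.11 with 4.7 and 4.6 is real and unresolved. Loss of the Day 43 sample after a failed Day 22 check is the likely reading of 12.11 with 4.7, not an express rule. It assumes that the failed item counts as a change in baseline condition and that early termination includes no research draw.

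The size is uncertain and probably small. The number of participants affected may be zero. One loss costs about 2 points of power. Bias arises only if removal is related to both arm and response, which the documents neither show nor exclude. Severity is minor; the point is worth making because the correction is cheap and carries out what 4.6 already intends.

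**What to change.** 1. In 12.11, change the consequence of no longer meeting a criterion from withdrawal to no further study agent.
2. In 12.11 or 6.4, state that such participants keep the scheduled Day 43 and Day 50 research draws and the safety follow-up, unless they refuse or the investigator judges a procedure (draw, mosquito feeding or biopsy) unsafe. Pregnancy stays under 12.4.4.
3. In 14.3, commit to reporting immunogenicity both with and without participants who missed dose 2, each in the assigned arm. The sponsor names which is primary, before unblinding.

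The cost is a few sentences, with no added participants or visits; both draws are already scheduled. The downside is that a few participants in the two-dose arms (Groups 2, 4 and 5) would contribute one-dose data to the as-randomized analysis and could dilute the two-dose response. Reporting both analyses makes that visible.

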### **12.12 Replacement of a Participant**

If a participant withdraws or appears ineligible to continue the study before vaccine/placebo administration, he/she will be removed and no data will be used in analysis or publication of the study. The participant may be replaced in the accrual with a new volunteer who qualifies and consents to the study, and who can complete both vaccinations 14-28 days before the planned date of mosquito challenge. Safety data from all participants that have withdrawn will be used and included in the safety analysis.

### **12.13 Safety Oversight**

#### **12.13.1 Safety Review and Communications Plan (SRCP)**

A Safety Review and Communication Plan (SRCP) has been developed for the protocol. The SRCP is an internal communications document between the PI and the CSO, which delineates the safety oversight responsibilities of the PI, the CSO, and other stakeholders. The SRCP also includes the overall plan for conducting periodic safety surveillance assessments.

### 12.13.2 Sponsor Medical Monitor

A Medical Monitor, representing the IND Sponsor (OCRPRO), has been appointed for oversight of safety in this clinical study. The Sponsor Medical Monitor will be responsible for performing routine safety assessments in an SRCP.

### 12.13.3 Data and Safety Monitoring Board

The NIAID intramural data and safety monitoring board (DSMB) includes independent experts that do not have direct involvement in the conduct of the study and have no significant conflicts of interest as defined by NIAID policy. The DSMB will review the study protocol, consent document(s), and investigator brochure prior to initiation and twice a year thereafter, or as may be determined by the DSMB.

The DSMB may convene additional reviews as necessary. The DSMB will review the study data as needed to evaluate the safety, efficacy, study progress, and conduct of the study.

All deaths, SAEs, UPs, pregnancies, and IND safety reports will be reported to the DSMB at the same time they are submitted to the IRB and CSO unless otherwise specified herein.

All cases of intentional or unintentional unblinding will be reported to the DSMB not later than one business day from the time of study personnel awareness.

The principal investigator will notify the DSMB at the time pausing or halting criteria are met and obtain a recommendation concerning continuation, modification, or termination of the study. The principal investigator will submit the written DSMB summary reports with recommendations to the IRB(s).

## 13 Site Monitoring Plan

According to the ICH-GCP 5.18 and FDA 21 CFR 312.50, clinical protocols are required to be adequately monitored by the study sponsor. This study monitoring will be conducted according to the sponsor's clinical monitoring guidelines. Clinical monitors will visit the clinical research site to monitor aspects of the study in accordance with the appropriate regulations and the approved protocol. The objectives of a monitoring visit will be:

- 1) To verify the existence of signed informed consent documents and documentation of the informed consent process for each monitored participant;
- 2) To verify the prompt and accurate recording of all monitored data points, and prompt reporting of all SAEs;
- 3) To compare clinical data abstracts with individual participants' records and source documents (participants' charts, laboratory analyses and test results, physicians' progress notes, nurses' notes, and any other relevant original participant information); and
- 4) To help ensure investigators are in compliance with the protocol. The monitors also will inspect the clinical site regulatory files to ensure that regulatory requirements (FDA; University of Maryland, Baltimore; Office for Human Research Protections [OHRP]) and applicable guidelines (ICH-GCP) are being followed. During the monitoring visits, the investigator (and/or designee) and other study personnel will be available to discuss the study progress and monitoring visit.

The investigator (and/or designee) will make study documents (e.g., consent forms, clinical data abstracts, and pertinent hospital or clinical records) readily available for inspection by the FDA, IRB, site monitors, and NIAID staff for confirmation of the study data.

A specific protocol monitoring plan will be discussed with the PI and study staff before enrollment. The plan will outline the frequency of monitoring visits based on such factors as study enrollment, data collection status, and regulatory obligations.

## 14 Statistical Considerations

### 14.1 Study Hypothesis

The study hypothesis is that:

- AGS-v PLUS specific immunoglobulin will increase after vaccination with AGS-v PLUS compared to placebo
- PBMCs collected after vaccination with AGS-v PLUS incubated with AGS-v PLUS antigens will show a greater Th1 response as compared to placebo vaccination. Interferon-gamma is the main cytokine marker for Th1 responses.

### 14.2 Sample Size Justification and Analysis Plan

The primary objective of this study is to evaluate safety.

For the safety endpoint we are interested in identifying the number of participants with at least one SAE that is possibly, probably or definitely related to vaccine (halting rule 1). With 10 participants in each group we would have an 80% chance of observing at least one participant with at least one SAE if the true underlying rate for that SAE in a vaccinated arm is 0.15. We will have a 10% chance of observing at least one SAE if the true underlying rate is .01. If we collapse across the vaccinated arms we would have 40 participants. With 40 participants we would have a 95% chance of observing at least one participant with AEs if the true rate is 0.07. There is a 4% chance of observing at least one SAE out of 40 if the true rate is .001. With this sample size we will have a high probability of beginning to see a severe adverse event safety signal if one exists. Table 1 shows the probability of observing at least one participant with an SAE for various true SAE rates with samples sizes of 10 and 40.

In halting rule 2 we will halt the study if at least 2 or more of the same or similar AE's (possibly, probably or definitely related to vaccine) that are grade 3 or above are observed. With 10 participants in each group we would have an 80% chance of observing 2 or more participant with at least one AE if the true underlying rate in a vaccinated arm is 0.27. We will have a less than a 1% chance of observing at least 2 AE if the true underlying rate is .01. If we collapse across the vaccinated arms we would have 40 participants. With 40 participants we would have an 84% chance of observing at least two participants with AEs if the true rate is 0.08. There is a 6% chance of observing at least two AE out of 40 if the true rate is .01. With this sample size we will have a high probability of beginning to see an adverse event safety signal if one exists. Table 2 shows the probability of observing at least one participant with an SAE for various true SAE rates with samples sizes of 10 and 40.

Since this is a Phase 1b study we are looking for activity of the vaccine that would indicate the vaccines should be studied further. Since we do not wish to expose more participants than necessary to an experimental vaccine but we also don't wish to miss an active vaccine we will design the study to have 85% power with a one sided type I error rate of 0.1. We will also not adjust for the multiple comparisons (4 active arms being compared to placebo).

With 10 participants per arm, there will be at least 85% power to detect a true difference in the primary immunogenicity endpoint of 0.95 standard deviations using a one-sided t-test with significance level of 0.1(R version 3.4.1).

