**Table 2. Probability of observing at least 2 SAE’s for samples sizes of 10 and 40 with different true SAE rates**

True rate of severe adverse events	Probability of observing at least 2AE’s (halting rule 2)	
	N=10	N=40
.01	<.001	.06
.08	.19	.84
.27	.80	>.99

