### 14.3 Analysis Plan

T-tests will be used to compare immunogenicity endpoint measurements for the primary endpoint and other continuous endpoints between each treatment group and the placebo group. For binary endpoints Fishers exact test will be used. AEs will be tabulated by treatment arm.

The fold increase in cellular and humoral responses to AGS-v PLUS from day 1 to days 43 and 50, and from day 43 to day 50 will be calculated for each participant. The mean fold increases on each active group will be compared to the mean fold increases in the placebo group. The geometric mean antibody titers and geometric mean cytokine concentrations to AGS-v PLUS on days 1, 43, and 50 will be calculated and compared between the different treatment groups.

The fold increase in cellular responses to mosquito saliva from day 1 to days 43 and 50, and from day 43 to day 50 will be calculated for each participant. The mean fold increases on each active group will be compared to the mean fold increases in the placebo group. The geometric mean cytokine concentrations to mosquito saliva on days 1, 43 and 50 will be calculated for each treatment group and compared to placebo.

For the mosquito analysis, the following parameters will be compared on the active groups versus placebo for each mosquito (*Aedes aegypti* and *Aedes albopictus*):

- mean number of days mosquitoes survive after feeding on vaccinated participants
- mean number of eggs laid
- mean number of mosquitoes emerging from the laid eggs

For the visual assessment of the mosquito bite the following parameters will be calculated for each group and active groups will be compared to placebo at three different time points: day 43 (30 min post feeding), day 45 and day 50:

- mean number of visible bites
- mean redness measured across the widest part (mm)
- mean swelling measured using the ball point pen method (mm^2). Ball point pen measurement of induration uses the pen to slide on top of the skin so it halts at the edge of true induration (versus redness)

From the biopsies taken on day 45, the following comparisons will be made:

-gene expression: the level of expression of inflammatory cytokines at the bite site compared to normal skin (control) will be calculated for each participant for each mosquito bite. The mean will be calculated in each group and compared to placebo.

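### The immunogenicity power statement is wrong: 10 per arm gives 79% power for a 0.95 SD difference, not at least 85%; 85% power needs 1.06 SD

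*Combined protocol and SAP*

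**What the plan says.** Section 14.2 sets the immunogenicity design target: "we will design the study to have 85% power with a one sided type I error rate of 0.1". It also declines a multiplicity correction: "We will also not adjust for the multiple comparisons (4 active arms being compared to placebo"). It then reports that 10 participants per arm meet the target: "at least 85% power to detect a true difference in the primary immunogenicity endpoint of 0.95 standard deviations using a one-sided t-test" at the 0.1 level, citing R version 3.4.1.

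Section 14.3 names the comparison as t-tests "between each treatment group and the placebo group". Section 3.1 gives equal allocation to five groups of 10.

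Table 2 in section 14.2, in the columns headed "Probability of observing at least 2AE"’s, prints <.001 for N=10 at a true rate of .01. The text of the same section gives that probability as below 1%.

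**The concern.** The four design inputs (10 per arm, 0.95 SD, one-sided 0.1, t-test) determine the power completely, and they do not give 85%. This is the only power statement for the immunogenicity primary endpoints. Section 14.2 presents it as the balance between exposing few people and not overlooking an active formulation.

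If the real power is lower, a non-significant arm is weaker evidence of inactivity than the plan tells its readers. A formulation could then be dropped with more confidence than the design supports.

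**Working it through.** **Inputs, all from the document**

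- n = 10 per arm, active and placebo (sections 3.1 and 14.2)
- standardised difference d = 0.95 (section 14.2)
- one-sided α = 0.1, no multiplicity adjustment (section 14.2)
- two-sample t-test, each active arm against placebo (section 14.3)

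**Step 1. Power at 0.95 SD, exact noncentral t**

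- Degrees of freedom: 10 + 10 − 2 = 18
- Critical value: t(0.90; 18) = 1.330
- Noncentrality: d / √(1/10 + 1/10) = 0.95 × √5 = 2.124
- Power = P(T > 1.330), where T is noncentral t with 18 df and noncentrality 2.124 = **0.786**

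A simulation of 400,000 trials gave 0.788. The stated figure of at least 0.85 is not reproduced; the shortfall is 85.0 − 78.6 = 6.4 percentage points. The miss rate is 1 − 0.786 = 0.214, and 0.214 / 0.15 = 1.4 times the stated risk.

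**Step 2. Difference that has 85% power**

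Solving the same expression for power 0.85 gives d = **1.061 SD**. This is 1.061 / 0.95 = 1.12 times the stated difference.

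**Step 3. Other ways to reach the printed figure**

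| Reading | Power at 0.95 SD | Fits sections 14.2 and 14.3? |
|---|---|---|
| Two-sample t, one-sided 0.1, 18 df | 78.6% | Yes |
| Same, normal approximation | 80.0% | Approximation only |
| Same, variance pooled over five arms, 45 df | 79.5% | Arguable |
| Two-sided 0.1 | 65.5% | No, one-sided stated |
| 12 per arm (accrual ceiling 60 / 5) | 84.2% | No, 10 stated |
| One-sided 0.15 | 85.4% | No, 0.1 stated |
| 40 pooled vaccinees vs 10 placebo | 91.7% | No, each arm vs placebo |
| Within-arm one-sample test, n = 10 | 94.3% | No, no placebo comparison |

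Only the last three rows reach 85%, and each contradicts the stated test. Section 14.2 collapses the vaccinated arms for the safety probabilities only.

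By the normal approximation, the difference with 80% power is (1.2816 + 0.8416) × √0.2 = 0.9495 SD. An 80% calculation may therefore have been labelled 85%. The document does not show how 0.95 arose, and by exact t the 80% difference is 0.972 SD. The conclusion does not depend on this.

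**Step 4. Sample size needed to keep 0.95 SD**

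With 12 per arm power is 84.2%; with 13 per arm it is 86.4%. So 13 per arm would be needed.

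**Step 5. Sensitivity to missing day 43 data (assumed, since no dropout rate is stated)**

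| Evaluable | Power at 0.95 SD |
|---|---|
| 10 vs 10 | 78.6% |
| 9 vs 9 | 75.2% |
| 8 vs 8 | 71.3% |

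**Step 6. Table 2, N=10, true rate .01**

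P(X ≥ 2) = 1 − 0.99¹⁰ − 10 × 0.01 × 0.99⁹ = 1 − 0.9044 − 0.0914 = **.0043** from unrounded terms. The table prints <.001. The other five cells reproduce: .06, .19, .84, .80 and >.99.

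**The case against.** The best reply concerns weight, not arithmetic. Section 14.2 opens by naming safety as the primary objective, and most of it, with Tables 1 and 2, supports the group size through the chance of seeing halting-rule events. The power sentence is thus a second justification for 10 per arm. The trial is an activity screen with a deliberately liberal error rate. No go/no-go rule is tied to 85% power, and the correction changes no participant number, test or visit. All of that stands and limits the consequences. It does not make the figure right: antibody and cellular responses are also a primary objective, and the plan sets a numerical target and reports meeting it.

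Section 14.2 does not use the term two-sample, and a pooled or within-arm comparison would exceed 85%. That does not stand, because sections 14.2 and 14.3 both specify each active arm against placebo.

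The attrition figures are open to fair challenge. The Protocol Summary separates 50 participants for analysis from a ceiling of 60, and sections 4.6 and 4.7 aim to keep following people who discontinue. Section 12.12 provides replacement only before vaccine or placebo is given, so later losses would lower power, but by how much is unknown. The conclusion rests on full data. The Table 2 cell is a small, separate slip, and the accompanying text is correct.

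**Conclusion.** The concern holds. The planned comparison has 78.6% power for 0.95 SD, about 6 percentage points below the stated minimum, and the 85%-power difference is 1.06 SD. The per-comparison risk of missing a true 0.95 SD effect is 21.4%, not 15% or less.

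This assumes normally distributed data with a common SD on the analysis scale and complete data in all 10 participants of both arms. The error must be fixed because the stated power is false as written; it does not undermine the trial's conduct. Separately, the Table 2 cell for N=10 at rate .01 should be .004.

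**What to change.** Keep 10 per arm and replace the power sentence in section 14.2 with wording such as: *With 10 participants per arm there is 85% power to detect a true difference of 1.06 SD (79% power for 0.95 SD) with a one-sided two-sample t-test at the 0.1 level, comparing each active arm with placebo.* In Table 2, change the N=10 entry at rate .01 from <.001 to .004.

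The cost is one sentence and one table cell. There are no extra participants and no change to the analysis; the stated sensitivity becomes slightly less favourable. The alternative of holding 85% power at 0.95 SD needs 13 per arm. That is 5 × 13 = 65 participants, above the accrual ceiling of 60, so restating the figure is the proportionate choice.
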